3.16.3.1.1. Weeks 4, 8, 12, 16, 20, and 24 (Visits 14 Through 19)

During the study drug treatment period, patients will return to the study center once every 4 weeks (± 7 days) thereafter (relative to DoR/baseline) for administration of study drug and assessments until the end of the treatment period (week 24 or early withdrawal).

The following procedures/assessments will be performed before administration of study drug unless otherwise indicated:

- Perform urine pregnancy testing at weeks 4, 8, 12, 16, 20, and 24 or early withdrawal
- Perform hematology tests (CBC with differential) at weeks 4, 8, 12, 16, 20, and 24 or early withdrawal
- Perform serum chemistry tests (weeks 12 and 24 or early withdrawal) (a sample for CPK measurement only will also be collected on weeks 4, 8, 16, and 20).
- Perform brief physical examination at weeks 4, 8, 12, 16, 20, and 24 or early withdrawal
- Perform vital signs measurements (includes systolic and diastolic blood pressure, pulse, body temperature, and respiratory rate) at weeks 4, 8, 12, 16, 20, and 24 or early withdrawal
- Measure height and weight (week 24 or early withdrawal) for patients 12 to <18 years of age
- Measure weight (week 24 or early withdrawal) for adult patients
- Perform ECG (week 24 or early withdrawal)
- Perform adverse event inquiry
- Complete asthma-specific tests
 - Provide and collect PEF meter (week 24 or early withdrawal)
 - Provide/collect electronic asthma control diary; reinforce diary and PEF compliance (weeks 4, 8, 12, 16, 20, and 24 or early withdrawal)
 - OCS reduction attempts (weeks 4, 8, 12, 16, and 20)
 - Pre-bronchodilator spirometry (weeks 4, 8, 12, 16, 20, and 24 or early withdrawal)
 - Post-bronchodilator spirometry (weeks 4, 12, 20, and 24 or early withdrawal)

- AQLQ +12 (weeks 4, 8, 12, 16, 20, and 24 or early withdrawal) (may be completed after study drug administration during the 1-hour observation period)
- ACQ-6 (weeks 4, 8, 12, 16, 20, and 24 or early withdrawal) (may be completed after study drug administration during the 1-hour observation period)
- Collect blood for asthma biomarker analysis (week 24 or early withdrawal)
- Assess CAEs and related health care utilizations
- Collect blood for serum reslizumab concentration determination (PK assessment) (weeks 4, 8, 12, 16, 20, and 24 or early withdrawal)
- Collect blood sample for immunogenicity assessment (weeks 4, 8, 12, and 24 or early withdrawal)
- [REDACTED]
- [REDACTED]

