7.1.7.3.2. Creatine Phosphokinase/Muscular Adverse Events CRF

Potentially clinically significant creatine phosphokinase (CPK) elevations (with or without associated symptoms) or myalgia/muscle symptoms will be recorded as an adverse event and documented using the potentially clinically significant CPK/myalgia case report form. A potentially clinically significant CPK is defined as $\geq 3.1 \times$ the upper limit of normal (ULN) (Grade 3 based on the Food and Drug Administration [FDA] “Guidance for Industry Toxicity Grading Scale for Healthy Adult and Adolescent Volunteers Enrolled in Preventative Vaccine Clinical Trials”).

If a potentially clinically significant CPK level ($\geq 3.1 \times$ ULN) occurs, the patient should attend an unscheduled visit for a physical examination and additional testing if indicated per investigator judgement. CPK levels will be re-tested at a minimum of every 7 to 10 days until the elevation is resolved, or if agreed with the medical monitor that no further testing is indicated. For $\geq 10 \times$ ULN elevations in CPK, repeat CPK level, urinalysis (including microscopy), serum electrolytes, BUN, and creatinine will be performed as soon as possible after receipt of the CPK result. Further testing of CPK levels should be undertaken as frequently as needed to manage patient care per investigator judgment, but should be at a minimum of every 7 to 10 days as above. Need for repeat urinalysis, serum electrolytes, BUN, and creatinine testing should be determined by the investigator. In addition, need for treatment (eg, administration of iv fluids and urine alkalinization) should be considered by the investigator.

In cases deemed by the investigator to be treatment-related elevations in CPK $\geq 10 \times$ ULN (eg, potentially rhabdomyolysis), study drug discontinuation should occur at least until CPK normalization or longer based on investigator clinical assessment.

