7.4. Vital Signs

Vital signs (pulse, blood pressure, body temperature, and respiratory rate) will be measured at time points specified in Table 5 and before other assessments (eg, blood draw and pulmonary function testing) and study drug administration. Vital signs include the following:

- pulse
- blood pressure
- body temperature
- respiratory rate

Before pulse and blood pressure are measured, the patient must be in a supine or semi-erect/seated position and resting for at least 5 minutes. The same position and arm should be used each time vital signs are measured for a given patient. For any abnormal vital sign finding, the measurement should be repeated as soon as possible. Any vital sign value that is judged by the investigator as a clinically significant change (worsening) from a baseline value will be considered an adverse event, recorded on the source documentation and transcribed onto the CRF, and monitored as described in Section 7.1.2.

In addition, potentially clinically significant values will be predefined by the sponsor for selected vital parameters and will be detailed in the statistical analysis plan.

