4.5. Study Days and Visit Windows

Study days will be numbered relative to the first day of study drug administration. The start of treatment (day 1) is defined as the date on which a patient takes the first dose of study drug, as recorded on the study drug diary. Days will be numbered relative to study start (ie, ..., -2, -1, 1, 2, ...) with day 1 being the start of study drug and day -1 being the day before the start of study drug).

For safety-by-visit summaries, if there are multiple assessments at a post-baseline visit then the last non-missing assessment at that visit will be used for the analysis. This includes assessments at the scheduled and unscheduled visits.

‘Endpoint’ for safety analyses and summaries is the time point when the last observation was obtained during the treatment period. For patients who completed treatment in this study, the treatment period will be defined from the first dose of study drug to the end of treatment (week 24) visit. For patients who prematurely discontinue treatment, the treatment period will be defined from the first dose of study drug to the last dose of study drug + 4 weeks.

For efficacy-by-visit summaries, only the assessments at the scheduled visit will be summarized. The assessments at unscheduled visits will be listed. For the purpose of the efficacy analysis, assessments collected at an early termination visit will be considered as the next scheduled visit for that assessment if at least 3 but no more than 5 weeks elapsed since the date of the last medication intake.

Efficacy-by visit summaries will be presented on-treatment. In this context, ‘endpoint’ will be defined as the last observation obtained at a scheduled or qualified early termination visit during the treatment period. For patients who completed treatment in this study, the treatment period will be defined from the first dose of study drug to the end of treatment (week 24) visit. For patients who prematurely discontinue treatment, the treatment period will be defined from the first dose of study drug to the last dose of study drug + 4 weeks.

For selected variables, additional sensitivity analyses may be presented utilizing all data collected over the entire course of the study including data collected after withdrawal for patients who prematurely discontinue from treatment. In this context, ‘endpoint’ will be defined as the last observation obtained at any post-baseline scheduled or qualified early termination visit.

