7.5. Clinical Laboratory Tests

Analysis of laboratory tests will be based on on-treatment results, as described in Section 7.1. Measurements collected outside of the defined treatment periods will be excluded. All results will be included in the patient listings.

Summary statistics for laboratory tests will be presented at baseline and at each scheduled visit. Actual values and changes from baseline to each visit will be summarized. Shifts (below, within, and above the normal range) from baseline to each visit will be summarized using patient counts and percentages. Shifts from baseline (Grade 0-4) will be provided for creatine phosphokinase (CPK) at each visit, based on the following grading scale:

- **Grade 0:** <1.25 x ULN
- **Grade 1:** 1.25 to 1.5 x ULN
- **Grade 2:** 1.6 to 3 x ULN
- **Grade 3:** 3.1 to 10 x ULN
- **Grade 4:** >10 x ULN

For CPK values $\geq 3.1 \times \text{ULN}$ (Grade 3-4), investigators will be prompted to collect additional information from the patient related to symptoms associated with the elevation and any potential alternate causes. This supplemental data will be reported in the patient listings.

The incidence of potentially clinically significant laboratory values will be summarized using the criteria specified in Table 11; criteria have been provided for adults and adolescents separately. Summaries of potentially clinically significant laboratory values will include all relevant post-baseline values (including scheduled, unscheduled, and early termination visits). A post-baseline laboratory value will be considered potentially clinically significant only if it satisfies the specified criteria and is more extreme (farther from the limit) than the baseline value. Listings for potentially clinically significant laboratory data will be presented. If any patient has a positive pregnancy test, relevant information will be supplied in data listings.

A scatter plot will be provided for the baseline and maximum on treatment value for CPK.

Table 11: Criteria for Potentially Clinically Significant Laboratory Values

Test	Adults (≥18 years)		Adolescents (12 to <18 Years)	
	Criterion value	Change from baseline	Criterion value	Change from baseline
Serum chemistry				
Alanine aminotransferase	≥3xULN	Increase >0	≥3xULN	Increase >0
Aspartate aminotransferase	≥3xULN	Increase >0	≥3xULN	Increase >0
Alkaline phosphatase	≥3xULN	Increase >0	≥3xULN	Increase >0
Gamma-glutamyl transpeptidase	≥3xULN	Increase >0	≥3xULN	Increase >0

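### The by-visit CPK grade shift table takes the last value at a visit, retests included, so it can show a later, usually recovered, value in place of the elevation

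*SAP*

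**What the plan says.** SAP Section 4.5 sets the rule for by-visit safety summaries: "if there are multiple assessments at a post-baseline visit then the last non-missing assessment at that visit will be used for the analysis". It adds: "This includes assessments at the scheduled and unscheduled visits". For efficacy the same section goes the other way: "For efficacy-by-visit summaries, only the assessments at the scheduled visit will be summarized".

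Protocol Section 7.1.7.3.2 sets the CPK follow-up. At 3.1 x ULN or more, "the patient should attend an unscheduled visit for a physical examination and additional testing if indicated per investigator judgement", and "CPK levels will be re-tested at a minimum of every 7 to 10 days until the elevation is resolved", unless the medical monitor agrees that no more testing is needed. For vital signs, Protocol Section 7.4 says only: "For any abnormal vital sign finding, the measurement should be repeated as soon as possible".

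The by-visit outputs that inherit the rule are in SAP Sections 7.5 and 7.6. They are the laboratory and vital-sign means and changes, the laboratory normal-range shifts, and the CPK grade shifts: "Shifts from baseline (Grade 0-4) will be provided for creatine phosphokinase (CPK) at each visit". In the same sections, the summaries of potentially clinically significant (PCS) values use every relevant post-baseline value, unscheduled ones included.

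**The concern.** Whether a CPK value is repeated depends mainly on the value itself. A normal scheduled CPK triggers no retest and stays in the table. A Grade 3 or 4 value starts a series of later values that is meant to run until recovery. Taking the last value of such a series is selection tied to the result, and it leans towards the recovered grade.

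CPK matters in this trial. Myalgia is listed as an adverse drug reaction of reslizumab (Protocol Section 1.3.2.2), and muscle disorders, including increased blood CPK, are an adverse event of special interest (SAP Section 7.3.1.5). A reader who wants to see how patients moved between CPK grades has only the by-visit shift table. If it understates elevations, it does so more in whichever arm has more of them, and it will not match the Grade 3-4 incidence for the same patients. With about 76 patients per arm, one patient is 1/76 = 1.3%. The documents give no expected Grade 3-4 rate, but if events are few, regrading one or two patients could empty a cell.

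**Working it through.** The plan states no figure to reproduce here. The check concerns timing: which retests can carry the label of the visit at which the elevation was found.

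**Inputs**
- Visit spacing (Protocol Section 3.16.3.1.1): "patients will return to the study center once every 4 weeks (± 7 days) thereafter". On nominal days, weeks 4, 8, 12, 16, 20 and 24 fall on days 28, 56, 84, 112, 140 and 168.
- CPK is drawn at all six of these visits: CPK alone at weeks 4, 8, 16 and 20, and full chemistry at weeks 12 and 24.
- Retest spacing is 7 to 10 days (Protocol Section 7.1.7.3.2).
- For completers, the treatment period ends at the week 24 visit, and laboratory values outside it are excluded (SAP Sections 7.1 and 7.5).
- No rule assigns unscheduled safety values to visits. Three conventions are assumed below.

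**Retests before the next visit**
- Every 7 days: +7, +14 and +21, so 3 fall before +28.
- Every 10 days: +10 and +20, so 2 fall before +28.

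**Visits at which a retest can replace the scheduled value**

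| Assumed assignment | 7-day retests | 10-day retests |
|---|---|---|
| Preceding scheduled visit | All 3 carry that visit's label; weeks 4-20, 5 of 6 | Both do; weeks 4-20, 5 of 6 |
| Nearest scheduled visit | The +7 retest stays with the visit (7 days against 21 to the next); 5 of 6 | The +10 retest stays with the visit (10 days against 18); 5 of 6 |
| Only within 7 days of a visit | The +7 retest is in the window; 5 of 6 | +10 and +20 are outside every window (the next opens at +21); 0 of 6 |

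**Week 24.** For completers the first retest would fall on day 168 + 7 = 175 or 168 + 10 = 178. Both are after the treatment period and are excluded, so the elevation stays under every convention. The same table can therefore treat week 24 differently from weeks 4 to 20.

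**Illustration.** Suppose a patient is Grade 0 at baseline, has a week 4 CPK in the Grade 3 range (3.1 to 10 x ULN), and is below 1.25 x ULN on day 35. Under all three conventions the week 4 shift reads Grade 0 to Grade 0. The PCS table counts the same patient as Grade 3.

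**Vital signs.** A repeat at the same visit replaces the first reading under any convention. SAP Section 7.6 plans no vital-sign shift table, so only by-visit means and changes are affected.

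**The case against.** The strongest answer is that the high values are reported elsewhere, and this stands. SAP Table 11 defines the CPK PCS criteria by Grade 3 and Grade 4, and that incidence uses all relevant post-baseline values. The maximum on-treatment CPK is plotted. CPK of at least 3.1 x ULN is recorded as an adverse event on a dedicated form, and all results are listed. A reader might infer that transient elevations vanish from the safety report, or that the shift table is the only graded CPK display. The documents support neither.

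A reader might also infer that every elevation resolving between visits will appear at its resolved grade. That needs a visit-assignment rule that the SAP does not give. Besides the 0 of 6 case above, a retest kept under its own unscheduled label would replace nothing, although the sentence on unscheduled visits would then have little to do. Retesting may also stop before resolution.

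The direction is not purely downward. Table 5 of the protocol also calls for CPK at the time of muscular adverse events, so a high unscheduled value can replace a normal scheduled one. For vital signs it is tempting to read a retest-until-resolved rule into the protocol. Section 7.4 asks only for a prompt repeat, which may confirm the abnormality, and vital signs are measured at unscheduled visits held for any reason. For other laboratory tests the protocol gives no retest schedule like the one for CPK.

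The core survives these points. The last-value rule is stated and CPK retesting depends on the result. The missing assignment rule leaves the programmer to decide how much is replaced.

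**Conclusion.** The point holds for CPK as a flaw in a descriptive safety display. The only planned baseline to post-baseline CPK grade shift, and the by-visit CPK means, can show a later and usually recovered value in place of the elevation. Exposure is 5 of 6 CPK visits if retests go to the preceding or nearest visit. Under a strict 7-day window it is 5 of 6 with 7-day retests or 0 of 6 with 10-day retests. It is none at week 24 for completers. These counts rest on nominal visit days and on the assumed assignment conventions. The number of patients affected cannot be derived from the documents. For vital signs only by-visit means are touched, and the direction is uncertain. Grade 3-4 incidence and the other safety outputs keep the abnormal values, and no efficacy result or type I error is affected. It is an inexpensive improvement worth making before unblinding.

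**What to change.** In SAP Sections 4.5 and 7.5:

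1. Use the scheduled-visit value for by-visit safety means and changes, as is already done for efficacy.
2. State how unscheduled safety assessments are assigned to visits.
3. Add one table of CPK grade shift from baseline to worst on-treatment grade, using all on-treatment values, scheduled and unscheduled. Alternatively, use the worst value per visit interval in the existing CPK shift table.

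The cost is a paragraph of SAP text, one extra table and minor programming; no new data are needed. The downside is that unscheduled values, including any high ones, leave the by-visit means. They remain in the worst-value, PCS and listing outputs.

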5. STUDY POPULATION

5.1. General

The ITT analysis set will be used for all study population summaries, unless otherwise noted. Population summaries will be presented by treatment group and overall.

5.2. Patient Disposition

Data from patients screened, patients screened but not randomized, and the reason the patients were not randomized will be summarized overall (for all screened patients). Patients randomized (ITT analysis set), patients randomized but not treated, patients in the safety analysis set, patients in the PP analysis set, patients who completed treatment (all 24 weeks while on study treatment), patients who completed the planned treatment phase (remained active in the study for the full 24 week duration, either on- or off-treatment), and patients who completed the study will be summarized. Patients will be categorized as completed the study if they either complete the study visits up to and including follow-up (Week 32, for patients not participating in the LTE study) or up to and including end of treatment (Week 24, for patients participating in the LTE study). Data from patients who withdrew early will be summarized by reason for withdrawal, and the number of patients who discontinued treatment but continued to attend study visits will be tabulated.

KM plots will be provided for time to discontinuation from treatment to identify if there is a differential dropout pattern between the treatment groups.

5.3. Demographics and Baseline Characteristics

Baseline demographics (eg, age, sex, race, ethnicity) and patient characteristics (eg, spirometry, airway reversibility) including smoking history, medical history, phadiatop test results, and prior medications will be summarized to assess the comparability of the treatment groups. Baseline stratification factors (age and optimized OCS dose) will also be summarized. Baseline demographics and patient characteristics will also be summarized separately for patients who discontinue from treatment and patients who complete treatment to investigate whether patients with and without missing values may have different characteristics at baseline.

Age will be calculated based on the date of birth relative to the screening visit (date of informed consent). If regional data regulations prohibit collection of a full date of birth, then the patient's age should be recorded on the CRF, if possible. If only a year of birth has been collected (and age has not otherwise been reported) then the missing date of birth will be imputed as 30 June (30 June YYYY) in order to derive the patient's age at baseline.

5.4. Medical History

All medical history abnormalities will be coded using the Medical Dictionary for Regulatory Activities (MedDRA). The incidence of medical history abnormalities will be summarized by system organ class (SOC) and preferred term (PT). Patients are only counted once in each SOC and once in each PT.

Asthma- and allergy-specific medical history, duration of oral corticosteroid use for asthma, and [REDACTED] will be collected and reported.

5.5. Prior Medications

All prior medications will be coded using the World Health Organization dictionary of medical codes (WHO Drug). The incidence of prior medications will be summarized by therapeutic class and preferred term. Patients are only counted once in each therapeutic class and once in each preferred term. Prior medications include all medications with a start date prior to the first day of study drug.

Prior medications for asthma will be summarized separately. In addition, total ICS dose taken at baseline will be summarized. The reported ICS doses will be converted to fluticasone equivalents using the following conversion factors. ICS dose at baseline will be defined as the dose taken at the time of randomization.

Table 7: Conversion of ICS to Fluticasone-Equivalent Doses

Inhaled corticosteroid (mcg)	Conversion factor
Fluticasone	1
Fluticasone furoate	2
Mometasone	1.14
Budesonide ^a	0.625
Ciclesonide	1.56
Beclomethasone	1.25
Triamcinolone	0.25

^a Nebulized budesonide is typically recorded in mg and, if applicable, the reported dose (in mg) may need to first be converted to mcg (x1000) prior to applying the indicated conversion factor for budesonide.

5.6. Electrocardiography

Electrocardiogram findings (normal, abnormal) at baseline will be summarized.

5.7. Physical Examinations

Patients with at least 1 abnormal finding (overall) and abnormal findings for each category will be summarized at baseline.

5.8. Protocol Violations

Patients with at least 1 protocol violation for each category will be summarized.

5.9. Childbearing Potential

For female patients, information related to childbearing potential, contraception, and menopause will be collected at screening. Information will be provided in the patient data listings.

6. EFFICACY ANALYSIS

6.1. General

The ITT analysis set will be used as the default patient population for all efficacy variables, unless otherwise noted. Summaries will be presented by treatment group as randomized.

6.2. Primary Efficacy Variable(s) and Analysis

6.2.1. Variable Definition

The primary efficacy variable for this study is the categorized percent reduction in the daily OCS dose during weeks 20 to 24 as compared with the OCS dose at the end of the optimization phase.

The week 20 to 24 maintenance dose and corresponding values for absolute and percent change (reduction) from baseline will be calculated as follows:

- **Baseline dose** = the prescribed optimized OCS dose following the OCS optimization period ([Table 8](#))
- **Maintenance dose** = mean of all daily OCS doses during the maintenance period extending from Week 20 to Week 24 ([Table 8](#))
- **Absolute reduction** = maintenance dose – baseline dose
- **Percent reduction** = $100 \times (\text{absolute reduction} / \text{baseline dose})$

For both the primary and secondary efficacy analyses, OCS dose will refer to the total daily dose of oral prednisone prescribed for asthma (as per CRF), unless otherwise noted.

The 5 categories for the primary analysis of percent reduction during weeks 20 to 24 are:

- 90% to 100% reduction
- 75% to <90% reduction
- 50% to <75% reduction
- >0% to <50% reduction
- No decrease in OCS, or loss of baseline asthma control during weeks 20 through 24, or discontinuation from study drug

Loss of baseline asthma control will be defined as FEV₁ value of <80% of baseline at the week 24 visit, or clinically significant worsening in ACQ-6 score (increase ≥ 0.5) at the week 24 visit compared with baseline, and/or clinical asthma exacerbation during weeks 20 through 24 (CAE defined in [Section 6.3.3.1](#)).

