The post-randomization period consists of the treatment period, follow-up visit and late follow-up visit. During the treatment period, the patient will continue his/her usual non-OCS background asthma medication without change; the OCS dose will be tapered per protocol. The treatment periods consist of an induction period and an OCS reduction period. During the induction period, the minimally effective dose of OCS will be maintained, unchanged, during the first 4 weeks of the treatment period. During the OCS reduction period, the minimally effective OCS dose will be reduced per protocol at scheduled clinic visits from the beginning of week 5 (ie, end of the induction period) through week 20. If the OCS dose could not be decreased, it should be held constant, or may be increased to a previous level, at the investigator's discretion, until the next study visit at which dose reduction criteria are met. This dose will be maintained for the final 4 weeks of the treatment period.

If a patient elects to withdraw (or is discontinued from treatment by the investigator), every attempt will be made to continue the assessments subsequent to his/her withdrawal from the study.

Method of Blinding and Randomization: Patients will receive sc placebo or reslizumab 110 mg on a 1:1 basis in a randomized, double-blind fashion. Randomization will be assigned using interactive response technology. After randomization, patients and investigators will remain blinded to randomized treatment assignment during the study. The sponsor's personnel involved in the study will be blinded to the study drug identity after the run-in period until the database is locked for analysis and the treatment assignment is revealed, with the exception of the bioanalytical group (Global Bioassays and Technology), who, in order to facilitate PK and ADA sample analysis, will not be blinded. Eosinophils and monocytes will be redacted from the from the post baseline differential cell count reports to avoid the possibility of removing the blind.

In order to achieve balance between treatment groups in regard to average daily OCS use/requirement, randomization will be stratified by optimized, average daily OCS dose of > 10 mg or ≤ 10 mg and age (12 to < 18 years of age or ≥ 18 years of age) at baseline.

Study Drug Dose, Mode of Administration, and Administration Rate: Reslizumab will be administered as a fixed dose of 110 mg, as a sc injection in the upper arm(s) once every 4 weeks.

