^a Baseline for clinic visit measures (FEV₁) is the DoR value. Baseline for diary measures is the average over the 7 days prior to DoR.

^b If a dose increase results in a return to the previous dose, then it is acceptable to attempt dose decrease again at the investigator's discretion.

AM=morning; DoR=date of randomization; FEV₁=forced expiratory volume in 1 second; PEF=peak expiratory flow; OCS=oral corticosteroid.

Table 3: Oral Corticosteroid Decrements During the Treatment Period

Time Course	Oral OCS Dose (mg/day)								
Optimized OCS dose	40	35	30	25	20	15	10	7.5	5
1 st reduction	30	25	20	15	10	10	7.5	5	2.5
+ 4 weeks	20	15	10	10	7.5	7.5	5	2.5	0
+ 4 weeks	10	10	5	5	5	5	2.5	0	
+ 4 weeks	5	5	2.5	2.5	2.5	2.5	0		
+ 4 weeks	2.5	2.5	0	0	0	0			

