6.3.2.1. Variable Definition

6.3.2.1.1. Continuous Variable

The post-baseline values for OCS dose and corresponding values for absolute and percent change from baseline will be calculated as follows:

- **Baseline dose** = the prescribed optimized OCS dose following the OCS optimization period (Table 8)
- **Post-baseline dose** = mean of all daily OCS doses during each defined analysis period (Table 8)
- **Absolute reduction** = post-baseline dose – baseline dose
- **Percent reduction** = $100 \times (\text{absolute reduction} / \text{baseline dose})$

Table 8: Definition of Analysis Days for OCS Dose

Analysis period	Start day	Stop day
Baseline Dose	Day of first dose of study drug	N/A
Baseline to Week 4	Day of first dose of study drug + 1 day	Day of W4 Visit
Week 4 to Week 8	Day of W4 Visit + 1 day	Day of W8 Visit
Week 8 to Week 12	Day of W8 Visit + 1 day	Day of W12 Visit
Week 12 to Week 16	Day of W12 Visit + 1 day	Day of W16 Visit
Week 16 to Week 20	Day of W16 Visit + 1 day	Day of W20 Visit
Week 20 to Week 24 (Maintenance Dose)	Day of W20 Visit + 1 day	Day of W24 Visit

DoR=Day of Randomization

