6.3.2.1.2. Categorical Variable

The proportion of patients achieving a 50% or greater reduction in OCS dose at weeks 20 to 24 will be based on the percent reduction from baseline to weeks 20 to 24. The categories for this analysis are:

- 50-100% reduction
- <50% reduction, or loss of baseline asthma control during weeks 20 through 24, or discontinuation from study drug

The proportion of patients who achieve a reduction of their OCS dose to less than or equal to 5 mg at weeks 20 to 24 will be based on the observed post-baseline value during weeks 20 to 24. The categories for this analysis are:

- ≤ 5 mg
- > 5 mg, or loss of baseline asthma control during weeks 20 through 24, or discontinuation from study drug

The proportion of patients who achieve a total reduction (discontinuation) of their OCS dose at weeks 20 to 24 will be based on the observed post-baseline value during weeks 20 to 24. The categories for this analysis are:

- =0 mg
- > 0 mg, or loss of baseline asthma control during weeks 20 through 24, or discontinuation from study drug

Note: Total reduction implies no OCS use during the entire period (weeks 20 to 24).

The proportion of patients achieving less than a 5 mg reduction in OCS dose at weeks 20 to 24 will be based on the absolute reduction from baseline to weeks 20 to 24. The categories for this analysis are:

- ≥ 5 mg reduction

- <5 mg reduction, or loss of baseline asthma control during weeks 20 through 24, or discontinuation from study drug

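### The weeks 20 to 24 mean OCS dose includes the week-24 visit day, and taper doses sit exactly on the endpoint cut-offs, so a prescription change dated that day can alter the primary category or a gated secondary

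*SAP*

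**What the plan says.** The protocol synopsis describes a dose reached by week 20: "This dose will be maintained for the final 4 weeks of the treatment period". Protocol 3.1.4 and SAP 2.1.4 likewise keep the dose unchanged from week 20 to the end-of-treatment visit, and no reduction attempt is scheduled at week 24.

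SAP 6.2.1 turns this into a number, the "mean of all daily OCS doses during the maintenance period extending from Week 20 to Week 24". SAP Table 8 runs the period from "Day of W20 Visit + 1 day" to "Day of W24 Visit". Section 6.2.1 also limits what counts: "OCS dose will refer to the total daily dose of oral prednisone prescribed for asthma (as per CRF), unless otherwise noted".

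The mean is then cut at these points:
- **Primary (6.2.1):** above 0%, 50%, 75% and 90%, each of the last three belonging to the better category.
- **Gated secondaries (6.3.2.1.2):** a reduction of at least 50%, a dose of at most 5 mg, a decrement of at least 5 mg, and 0 mg. For 0 mg the SAP adds a note that the patient must be free of OCS throughout the period.

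I found no rounding, tolerance or held-dose rule. Loss of asthma control is judged partly on FEV₁ and ACQ-6 at the week-24 visit.

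**The concern.** A mean equals the held dose only if every day in the window carries that dose. The last day of the window is the visit at which FEV₁ and ACQ-6 are assessed and the planned maintenance ends. A new prescription dated that day is no longer part of the maintenance being assessed, yet Table 8 counts it.

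This would hardly matter if the achievable doses lay well away from the cut-offs. They do not: the steps in Table 3, "Oral Corticosteroid Decrements During the Treatment Period", repeatedly land on 50%, 75%, 5 mg and a 5 mg decrement. Any single higher day then puts the mean on the wrong side. Four of the six secondaries are such cuts, and they include the first two in the fixed sequence, where one p-value above 0.05 stops all later testing.

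**Working it through.** **1. The plan's own figure.** Inputs from SAP 2.3 and 4.3: placebo distribution 10.9 / 7.9 / 14.8 / 10.8 / 55.6% (best to worst), odds ratio (OR) 2.63, two-sided alpha 0.05, power 90%, 1:1 allocation. Applying the odds ratio to the cumulative proportions gives 24.3 / 13.5 / 19.3 / 10.6 / 32.3% on reslizumab. With the Whitehead formula and the category proportions averaged over the two arms (p̄):

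N = 12 (1.960 + 1.282)² / [(ln 2.63)² (1 − Σp̄³)] = 126.1 / (0.935 × 0.902) = 149.4, or 75 per group.

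A tie-corrected Wilcoxon simulation at 76 per group gives 90.0% power. The stated 76 is reproduced.

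**2. One visit-day record.** The window is nominally 28 days. Reduction is taken as positive, as the categories require. With 27 days at the held dose and one day at the next higher step of Table 3:

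| Baseline → held (mg) | Mean (mg) | Reduction | Without that day |
|---|---|---|---|
| 10 → 5 | (27×5 + 7.5)/28 = 5.09 | 49.11% | 50% |
| 20 → 5 | (27×5 + 7.5)/28 = 5.09 | 74.55% | 75% |
| 25 → 2.5 | (27×2.5 + 5)/28 = 2.59 | 89.64% | 90% |

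Each drops one primary category. The first also fails the 50% reduction, the 5 mg dose and the 5 mg decrement.

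**3. All of Table 3.** It has 5+5+5+5+5+5+4+3+2 = 39 baseline-by-reduced-dose cells.
- **Primary category:** 9 change. At 50%: 40→20, 20→10, 15→7.5, 10→5, 5→2.5. At 75%: 40→10, 20→5, 10→2.5. At 90%: 25→2.5.
- **At least 50%:** 5 change (the same five as above).
- **At most 5 mg:** 8 change (5 mg reached from each of 40, 35, 30, 25, 20, 15, 10 and 7.5 mg).
- **5 mg decrement:** 4 change (15→10, 10→5, 7.5→2.5, 5→0).
- **0 mg:** 7 change.

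The union without the 0 mg rule is 9 primary cells, plus 6 new ones from the 5 mg dose, plus 3 new ones from the decrement: 18 of 39. The 0 mg rule adds 6, giving 24. The other 15 do not change. The counts are the same for windows of 14 and 42 days (the extremes of the ±7-day visit windows) and for a single day only 2.5 mg higher.

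**4. Effect on the comparison.** The documents give no frequency, so this is an assumption: a share q of patients in the 75 to <90% and 50 to <75% categories slips one category. This is generous, because only some patients in those categories sit on a cut-off. At q = 10%, the proportion with at least 50% reduction becomes:
- placebo: 0.336 − 0.10 × 0.148 = 0.321 (odds 0.473)
- reslizumab: 0.571 − 0.10 × 0.193 = 0.552 (odds 1.231)

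The odds ratio at that cut is 1.231/0.473 = 2.60. If only reslizumab slips it is 1.231/0.506 = 2.43. The common odds ratio comes from fitting the proportional odds model to the shifted proportions, and power from the simulation in step 1:

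| q | Common OR, both arms | Power, both arms | Common OR, reslizumab only | Power, reslizumab only |
|---|---|---|---|---|
| 2% | 2.63 | 89.9% | 2.61 | 89.3% |
| 10% | 2.62 | 89.7% | 2.55 | 88.1% |
| 20% | 2.61 | 89.5% | 2.48 | 86.5% |

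**The case against.** The opposing case is strong on exposure, and most of it stands.

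- **Only prescriptions count.** A reader might infer that a missed or extra tablet moves the category. It does not: the variable is the prescribed dose on the CRF.
- **The dose is meant to be stable.** Table 8 starts every later period on the day after a visit, which suggests that visit-day changes are usually dated from the next day. The week-24 problem arises only if a site dates one on the visit itself. The SAP does not settle this.
- **Nothing says another regimen starts on that day.** Protocol 3.16.4 places standard care after termination of the study, and the extension is conditional on being available. A visit-day change is possible, not expected.
- **A mean is a fair reading of the endpoint.** A reader might infer that the endpoint should be the dose at week 24, so that a week-20 cut later reversed is misclassified. The protocol defines the reduction during weeks 20 to 24, so a patient below baseline for part of that time is literally in the >0% to <50% category.
- **The 0 mg rule is deliberate.** Cells affected only through it are not an oversight.
- **Less exposed analyses exist:** the continuous percent change, itself a gated secondary, and the Wilcoxon rank analysis in SAP 6.3.2.2.3. Neither protects the primary or the binary secondaries.

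Replacing the mean by the modal dose would be a real change of endpoint. With baseline 15 mg, 14 days at 7.5 mg and 13 at 10 mg, the mode gives 50%, while the mean is (105 + 130)/27 = 8.70 mg, a 42% reduction, and the last dose is a 33% reduction. A mode would also conflict with the 0 mg note. That is a reason to use it only as a sensitivity analysis.

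**Conclusion.** The point holds in a limited form. Table 8 lets a prescription dated on the week-24 visit into an endpoint whose cut-offs coincide with taper doses. One such record changes the primary category in 9 of 39 cells, and the primary or a gated secondary in 18 of 39 without those reached only through the 0 mg rule. These are table cells, not patients; the share of patients in them is unknown.

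Two stronger conclusions are not supported. The trial is not materially underpowered by this: the loss is under 1 point at 20% slippage in both arms, and about 3.5 points only if slippage is confined to reslizumab, which nothing in a double-blind plan suggests. Nor does it favour reslizumab: upward changes can affect only patients who reduced, so if they concentrate in the arm that tapers better they pull towards no effect. All of these sizes rest on assumed slippage rates.

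The case for acting is that the endpoint should not depend on how a site dates a visit-day prescription, and that settling it costs almost nothing.

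**What to change.** Before unblinding, amend the SAP as follows:

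1. In Table 8, end the Week 20 to Week 24 period on the day before the week-24 visit, for all OCS endpoints.
2. Keep the mean as the definition in 6.2.1 and 6.3.2.1, and keep the 0 mg note in 6.3.2.1.2 as it is.
3. Add one sensitivity analysis of the categorical endpoints using the modal (longest-held) prescribed dose in that window, with ties assigned to the higher dose. One deviating day then changes none of the 39 cells. This also shows how far other short departures matter, such as a week-20 step recorded late or a brief oral increase that does not meet the exacerbation definition; the new stop day alone does not remove these.

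The cost is a window one day shorter (27 days nominally) and one extra table. No new data are needed, and the sample size stays at 76 per group.
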